6.8.6. Prior and Concomitant Medications and Nondrug Treatments

Prior and Concomitant medications will be coded by class and preferred term using the World Health Organization (WHO) Drug Dictionary.

Prior medications are medications used before the first dose of study drug. Concomitant medications are medications that were taken on or after first dose of study drug.

The number and percentages of patients who receive the following prior and concomitant medications will be summarized by class and preferred term by Cohort A for the ITT/Safety Population and mITT Population:

- Prior medications.
- Concomitant medications.
- Prior systemic mold antifungals.
- Other Licensed Antifungal Treatments that were optionally prescribed by investigator after 6 week of study drug treatment (this data has been collected in the prior antifungal module).
- Concomitant systemic mold antifungals.

In addition, duration of prior systemic antifungals prior to first dose of study drug will be tabulated in the following categories: 1 day, 2 days, 3 days, 4 days, 5 days, and >5 days.

All prior and concomitant medications and procedures will be listed by patient.

6.8.7. Safety Summaries and Analyses

Safety data will be summarized based on the Safety Population for Cohort A.

6.8.8. Adverse Events

An overview of AEs will be provided including counts and percentages of patients (and event counts) with the following:

- Any AEs.
- Any TEAEs (overall and by maximum severity).
- Any study drug related TEAEs (overall and by maximum severity).
- Any serious AEs (SAEs).
- Any treatment-emergent SAEs (TESAEs).
- Any TRSAEs).
- Any TEAEs leading to discontinuation of study drug.
- Any TRAEs leading to discontinuation of study drug.
- Any AEs leading to death.

The number and percentage of patients who experienced at least one TEAE will be presented by SOC and PT. TEAEs, TRAEs, study drug withdrawals due to TEAEs and TRAEs, and all SAEs will be summarized in the same manner.

Summaries will be provided by worst grade for the number and percentage of patients with TEAEs and TRAEs by SOC and PT.

Although a patient may have two or more TEAEs, the patient is counted only once within a SOC and PT category. The same patient may contribute to two or more PTs in the same SOC category.

A list of patients who have SAEs, a list of patients who discontinue from study drug due to TEAEs or TRAEs, and a list of death due to AEs will be provided. All AEs will be listed.

6.8.9. Laboratory Data

Central laboratory test results (chemistry, hematology, coagulation, and urinalysis) at each scheduled visit and change from baseline will be summarized with descriptive statistics.

Shift tables from baseline to each scheduled post-baseline visit will be provided for selected chemistry parameters (ALT, AST, ALP, Total Bilirubin, Creatinine, and Creatinine Kinase) and hematology parameters (Hematocrit, Hemoglobin, Platelets, White blood cell count and differential). For chemistry parameters, the following categories will be used: < the lower limit of normal (LLN), normal, >ULN to \le 2×ULN, >2×ULN to \le 3×ULN, >3×ULN to

≤5×ULN, >5×ULN, and missing. For hematology parameters, the following categories will be used: low, normal, high, and missing.

The number and percentage of patients with the following potentially clinically significant abnormal liver function tests at any post-baseline visit will be summarized:

- ALT \geq 3×ULN.
- ALT \geq 5×ULN.
- ALT \geq 10×ULN.
- AST $\geq 3 \times ULN$.
- AST ≥5×ULN.
- AST $\geq 10 \times ULN$.
- ALT or AST $\geq 3 \times ULN$.
- Total Bilirubin >1.5×ULN.
- Total Bilirubin >2×ULN.
- ALP \geq 1.5×ULN.
- ALP $\geq 2 \times ULN$.
- ALT or AST $\ge 3 \times ULN$ and Total Bilirubin $> 1.5 \times ULN$.
- ALT or AST >3×ULN and Total Bilirubin >2×ULN.
- Potential Hy's Law cases: ALT or AST ≥3×ULN and Total Bilirubin >2×ULN, and ALP ≤2×ULN.

A listing of patients with any post-baseline clinically significant abnormal liver function tests will be presented.

All clinical laboratory data will be listed. Values outside the normal ranges will be flagged.

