#### Assessment of Severity:

The severity of all adverse events should be graded according to the CTCAE v5.0. For those adverse event terms not listed in the CTCAE, the following grading system should be used:

- CTCAE Grade 1: Mild; asymptomatic or mild symptoms; clinical or diagnostic observations only; intervention not indicated
- CTCAE Grade 2: Moderate; minimal local or noninvasive intervention indicated; limiting age-appropriate instrumental activities of daily living
- CTCAE Grade 3: Severe or medically significant but not immediately life-threatening; hospitalization or prolongation of hospitalization indicated; disabling; limiting self-care activities of daily living
- CTCAE Grade 4: Life threatening consequences; urgent intervention indicated
- CTCAE Grade 5: Death related to the adverse event

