# APPENDIX E: REVISION AND UPDATE OF THE CONSENSUS DEFINITIONS OF PROBABLE INVASIVE FUNGAL DISEASE FROM THE EORTC/MSGERC

A diagnosis of probable IFD requires at least 1 Host Factor, 1 Clinical Criterion, and Mycological Evidence	
as described below: Host Factors	

 
Recent history of neutropenia (<0.5 × 10^9 neutrophils/L [<500 neutrophils/mm^3] for >10 days) temporally related to the onset of fungal disease
 
	
Hematologic malignancy	
Receipt of an allogeneic stem cell transplant	
Receipt of a solid organ transplant	

 
Prolonged use of corticosteroids (excluding among patients with allergic bronchopulmonary aspergillosis) at a therapeutic dose of ≥0.3 mg/kg corticosteroids for ≥3 weeks in the past 60 days
 
	

 
Treatment with other recognized T cell immunosuppressants, such as calcineurin inhibitors, TNF-α blockers, lymphocyte-specific monoclonal antibodies, or immunosuppressive nucleoside analogues during the past 90 days
 
	
• Treatment with recognized B-cell immunosuppressants, such as Bruton's tyrosine kinase inhibitors, eg, ibrutinib	

 
Inherited severe immunodeficiency (such as chronic granulomatous disease, STAT 3 deficiency, or severe combined immunodeficiency)
 
	

 
Acute GVHD Grade III or IV involving the gut, lungs, or liver that is refractory to first line treatment with steroids
 
	
Clinical Criteria	
Pulmonary aspergillosis	
The presence of one of the following 4 signs on CT:	
• Dense, well-circumscribed lesion(s) with or without a halo sign	
• Air-crescent sign	
• Cavity	
Wedge-shaped and segmental or lobal consolidation	
Other pulmonary mold diseases	
The presence of one of the following 5 signs on CT:	
• Dense, well-circumscribed lesion(s) with or without a halo sign	
• Air-crescent sign	
• Cavity	

 
Wedge-shaped and segmental or lobal consolidation
 
	
Reverse halo sign	
Tracheobronchitis	
Tracheobronchial ulceration, nodule, pseudomembrane, plaque, or eschar seen on bronchoscopic analysis	
Sino-nasal diseases	

 
Acute localized pain (including pain radiating to the eye)
 
	
Nasal ulcer with black eschar	

 
Extension from the paranasal sinus across bony barriers, including into the orbit
 
	
Central nervous system infection	
1 of the following 2 signs:	
Focal lesions on imaging	
Meningeal enhancement on magnetic resonance imaging or CT	

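### Hematology shift tables stop at low/normal/high, so worsening in patients already low at baseline does not show, and no graded or worst-post-baseline count summary is planned

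*SAP*

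**What the plan says.** SAP section 6.8.9 plans these laboratory outputs for Cohort A:

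- **Summaries by visit.** "Central laboratory test results (chemistry, hematology, coagulation, and urinalysis) at each scheduled visit and change from baseline will be summarized with descriptive statistics". SAP section 5.3.4 makes these n, mean, standard deviation, median, minimum and maximum.
- **Shift tables.** "Shift tables from baseline to each scheduled post-baseline visit will be provided for selected chemistry parameters", and also for "hematology parameters (Hematocrit, Hemoglobin, Platelets, White blood cell count and differential". Chemistry has four bands above the upper limit of normal. For blood counts: "For hematology parameters, the following categories will be used: low, normal, high, and missing".
- **Threshold counts.** These cover the liver only: patients with "potentially clinically significant abnormal liver function tests at any post-baseline visit will be summarized".
- **Listings.** "All clinical laboratory data will be listed. Values outside the normal ranges will be flagged".

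Adverse events are a separate route. In Protocol section 8.1.3, "The severity of all adverse events should be graded according to the CTCAE v5.0", and SAP section 6.8.8 tabulates treatment-emergent events by worst grade.

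On the population, the Protocol Appendix E host factors include "Hematologic malignancy", recent neutropenia and allogeneic stem cell transplant. Protocol section 4.2 sets hepatic and renal limits for entry but no blood-count limit.

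**The concern.** A shift table counts patients who got worse. With a single category below normal, it has nothing to record for a patient who starts there. A platelet or neutrophil count that is slightly low on Day 1 and very low on Day 14 is tabulated in the same cell as one that never changed. For patients who start in the normal range, a trivial dip and a deep fall also share one cell.

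This matters because safety is part of the primary objective (Protocol section 2.1), and many of the patients are likely to enter with depressed counts. There is no control arm, so a count of patients by objective severity is the hematology output that depends least on anyone's attribution. The plan does not contain one.

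**Working it through.** The plan states no figure on this point, so there is none to reproduce. The check has three parts.

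**1. What the categories allow.** Apart from missing, a patient is low, normal or high at baseline and at each visit.

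- Low at baseline: the only possible movements are none or upward. Further worsening cannot be seen.
- Normal or high at baseline: a fall below the lower limit is seen, but its depth is not.
- Shifts are by scheduled visit. No row takes each patient's worst value.

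**2. What the other outputs add.**

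| Output | What it shows | What it leaves out |
|---|---|---|
| Mean or median change by visit | Central tendency | Recovery in some patients can offset falls in others |
| Minimum value and minimum change by visit | The deepest value and the largest fall | How many patients fell, and from what starting level |
| Flagged listing | Every value | Any count by severity; a low flag marks mild and severe alike |
| Adverse events by worst grade | A graded patient count | Falls that the investigator did not report as an event |

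On the last row, Protocol section 8.1 asks for clinically significant abnormalities that are present at first dose and then worsen significantly to be reported as adverse events. The triggers are a required intervention, action on study drug, or the investigator's clinical judgment. The route exists, but it is filtered by judgment.

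**3. Possible size.** Inputs: N = 40 (the Cohort A maximum, SAP section 2.3); q = share low at baseline for a given cell line; f = share with a severe fall. The documents give neither q nor f. I assume q from 30% to 90%, f = 20%, and falls unrelated to baseline status.

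- No lower category available: N × q
- Able to show a new low: N × (1 − q)
- Severe falls hidden as low-to-low: N × f × q
- Severe falls shown as an ungraded new low: N × f × (1 − q)

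With f = 20% there are 40 × 0.20 = 8 severe falls:

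| q | No lower category | Can show a new low | Hidden | Shown, ungraded |
|---|---|---|---|---|
| 30% | 12 | 28 | 2.4 | 5.6 |
| 50% | 20 | 20 | 4.0 | 4.0 |
| 70% | 28 | 12 | 5.6 | 2.4 |
| 90% | 36 | 4 | 7.2 | 0.8 |

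At f = 10% the hidden number runs from 1.2 to 3.6, and at f = 30% from 3.6 to 10.8. Under these assumptions the hidden share equals q whatever f is. The falls that do show carry no severity in this table at any q.

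**The case against.** The other side has four fair arguments.

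- **Worsening from a low baseline is not ignored.** The adverse event rules in Protocol section 8.1 address it, and SAP section 6.8.8 tabulates the events by worst grade. Minima cannot be cancelled by recovery elsewhere, and a listing of at most 40 patients can be read one by one. This stands in part. The reader can find a severe fall, but must either rely on what was reported as an event or build the count by hand.
- **The finer liver categories follow the identified risk.** Protocol section 1.2.1 names liver toxicity and does not name marrow. This stands as an explanation of the asymmetry. It lowers the urgency, but does not make the table more informative.
- **A graded table could not separate drug from disease.** In an uncontrolled study that enrolls patients with hematologic malignancy, this is true and remains true after any fix.
- **The share low at baseline is unknown.** This stands. Solid organ transplant and prolonged corticosteroids also qualify a patient and do not imply low counts. The neutropenia criterion concerns recent history. Proven cases (Appendix D) need no host factor.

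A reader might infer that most patients start low. The documents make low counts likely in many, but give no figure, and the share will differ by cell line.

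**Conclusion.** The limitation is real and confined to safety reporting. For patients low at baseline, the hematology shift table cannot show further worsening. For the others it does not separate a mild new low from a severe one. No graded or worst-post-baseline summary fills the gap, and the remaining outputs do so only in part.

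A reader might go further and conclude that the plan cannot reveal marrow toxicity. The documents do not support that: new lows still appear in patients who were normal or high at baseline, and minima, listings and graded adverse events give other views.

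The table logic rests on no assumption. The counts do: 12 to 36 of 40 patients without a lower category, and 2.4 to 7.2 of 8 severe falls hidden, depend on an assumed 30% to 90% low at baseline, an assumed 20% rate of severe falls, and independence between the two. They show the possible scale and are not estimates. The primary efficacy analysis is unaffected. This is a cheap improvement, not an error that invalidates an analysis.

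**What to change.** Keep the low/normal/high table by visit; replacing it would lose the high category. Add to SAP section 6.8.9 a shift table of baseline CTCAE v5.0 grade, low direction, against worst post-baseline grade, for hemoglobin, platelets, white cells, neutrophils and lymphocytes. State the numerical limits used for each analyte, and whether unscheduled and early termination values count toward the worst grade. The protocol names this scale for adverse events, so the SAP must say explicitly that it is also applied to laboratory values.

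The data are already collected: Protocol section 8.7 schedules hematology at Screening, Days 1, 7, 14, 28 and 42, EOST and early termination. The cost is SAP text, some programming and a few extra tables. Two limits remain: a patient already in the lowest grade at baseline still cannot shift, and without a control arm the table cannot attribute a fall to the drug.

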# 4.2 Exclusion Criteria

Patients who meet any of the following criteria will not be eligible for the study:

- 1. Refractory hematologic malignancy with no potential to respond to additional chemotherapy.
- 2. Chronic aspergillosis, aspergilloma, or allergic bronchopulmonary aspergillosis.
- 3. Treatment with systemic (PO, IV, or inhaled) antifungal therapy with a mold-active azole or polyene for ≥120 hours immediately before initial dosing.

**Note**: An exception is antifungal prophylaxis, for which there is no restriction on duration but must be stopped upon commencement of treatment with APX001.

Additionally, patients with invasive fungal infection caused by a mold with documented resistance to or lack of coverage by the prior SOC in question, as well as patients with polyene-induced renal toxicity or those who have received empirical treatment with echinocandins may have received >120 hours prior treatment and remain eligible for the study. These patients must be discussed with the Medical Monitor prior to enrollment, and prior treatment in this case should not exceed >168 hours.

- 4. Evidence of significant hepatic dysfunction, defined as any of the following:
  - Total bilirubin >3 × the upper limit of normal (ULN) unless isolated hyperbilirubinemia or due to documented Gilbert's disease.
  - Alanine transaminase or aspartate transaminase  $\geq 5 \times ULN$ .
  - Severe or moderate hepatic impairment (Child-Pugh Score >6 points) at any time during 2 weeks prior to dosing. The Child-Pugh score of > 6 is applicable only to patients with hepatic dysfunction and cirrhosis.
- 5. Ongoing medical history of neurological disorders including abnormal movements or seizures. **Note:** A current CNS mold infection as well as a stable history of peripheral neuropathy will not be considered exclusionary.
- 6. Patient receiving palliative care only.
- 7. Known hypersensitivity or other serious reaction to APX001 or any ingredient of APX001.
- 8. Patient is lactating and/or pregnant or intending to be pregnant during the duration of the study.

9. Investigational drug administered within 30 days or 5 terminal half-lives prior to study drug dosing (whichever is longer).

**Note**: Participation in research protocols for approved agents for the treatment of an underlying condition is permitted.

- 10. Prior participation in this study or any previous study of APX001.

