## For patients with elevations in baseline transaminases or bilirubin:

If patients with abnormal baseline liver indices develop elevations of AST or ALT >2 x baseline or TBL >2 x baseline values during the study, repeat testing should be performed within 48 to 72 hours. Investigators should also ask to the patient if he/she has symptoms.

If there are persistent elevations (ALT or AST >2x baseline or TBL >2x baseline values) upon repeat testing, then close observation (as described below) should be implemented and discontinuation of drug should be considered.

Drug should be discontinued, and the patient followed until resolution of symptoms or signs in the following situations:

- If baseline measurements were <2x ULN, discontinue if ALT or AST increases to >5x baseline measurements.
- If baseline average measurements >2x ULN, discontinue if ALT or AST increases to >3x baseline measurements.
- Discontinue if ALT or AST increase >2x baseline measurements AND the increase is accompanied by a concomitant increase in TBL to >2x baseline measurements or the INR concomitantly increases by >0.2.

• For any patients who present with a constellation of syndromes indicative of liver disease as per the Investigator's overall assessment (ie, fatigue, nausea, vomiting, right upper quadrant pain or tenderness, fever, rash, and/or eosinophilia [>5%]).

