5.3.3. Definition of Baseline

For microbiological data, baseline pathogen(s) are *Aspergillus* spp. or rare molds (eg, *Scedosporium* spp., *Fusarium* spp., *Lomentospora* spp., and Mucorales fungi, etc.) isolated from the last positive fungal culture sample collected prior to the first dose of study drug.

For all efficacy and safety endpoints, baseline is defined as the last measurement or assessment prior to first dose of study drug.

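### The liver-test counts in SAP 6.8.9 ignore baseline, so an eligible patient whose values never change can be counted, including as a potential Hy's Law case, and no planned summary separates this out for the combined criteria

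*SAP*

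**What the plan says.** SAP 6.8.9 lists 14 criteria and says that the number and percentage of patients with "potentially clinically significant abnormal liver function tests at any post-baseline visit will be summarized". Eleven criteria concern transaminases, bilirubin or ALP without combining transaminases with bilirubin. Two combine ALT/AST with bilirubin. The last is "Potential Hy's Law cases: ALT or AST ≥3×ULN and Total Bilirubin >2×ULN, and ALP ≤2×ULN". All are multiples of ULN. None requires a rise from baseline or the absence of the abnormality at baseline, and none is split by baseline status. SAP 6.8.7 applies the safety summaries to the Safety Population of Cohort A, with no restriction on baseline liver values.

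SAP 5.3.3 does define a reference point: "baseline is defined as the last measurement or assessment prior to first dose of study drug". The flags do not use it. Other outputs in 6.8.9 do: descriptive change from baseline by visit, and "Shift tables from baseline to each scheduled post-baseline visit will be provided for selected chemistry parameters", which include ALT, AST, ALP and total bilirubin. Section 6.8.9 also plans a listing of patients with clinically significant abnormal liver tests and a listing of all laboratory data.

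Protocol 4.2, exclusion 4, sets the liver limits at entry. For "Alanine transaminase or aspartate transaminase" the patient is excluded at 5×ULN or above. For bilirubin the exclusion is "Total bilirubin >3 × the upper limit of normal (ULN) unless isolated hyperbilirubinemia or due to documented Gilbert's disease". ALP has no limit.

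Protocol Appendix H treats patients with raised baseline values separately and refers to their own baseline. Its text for them begins: "If patients with abnormal baseline liver indices develop elevations of AST or ALT >2 x baseline".

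**The concern.** The entry limits lie above several of the reporting thresholds. A patient can therefore cross a threshold before the first dose, stay exactly where they were, and still be counted in a post-baseline table. Nothing in that table distinguishes this patient from one whose liver tests became abnormal on treatment.

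This matters because Protocol 1.2.1 names liver toxicity as a potential risk, and because there is no control arm against which background abnormality could be judged. With about 40 patients planned for Cohort A, each patient is 1/40 = 2.5 percentage points. One or two unchanged patients in the Hy's Law row could change how the liver profile is read.

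**Working it through.** The documents state no figure on this point, so there is none to reproduce. The check is logical: take a patient who passes the liver limits in exclusion 4, hold every post-baseline value equal to the entry value, and see which of the 14 criteria in SAP 6.8.9 are met. All values below are multiples of ULN.

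**Step 1. Ranges open at entry.** ALT and AST: below 5. Bilirubin: up to 3, or above 3 if exempt. ALP: unrestricted.

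**Step 2. Each criterion against those ranges, with no change after entry.**

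- ALT ≥3; AST ≥3; ALT or AST ≥3: can be met (entry values from 3 to just under 5). 3 flags.
- Bilirubin >1.5; bilirubin >2: can be met. 2 flags.
- ALP ≥1.5; ALP ≥2: can be met. 2 flags.
- ALT or AST ≥3 with bilirubin >1.5; ALT or AST >3 with bilirubin >2: can be met. 2 flags.
- Potential Hy's Law (ALT or AST ≥3, bilirubin >2, ALP ≤2): can be met. 1 flag.
- ALT ≥5, ALT ≥10, AST ≥5, AST ≥10: cannot be met, because such values are excluded at screening, unless they rise between screening and first dose. 4 flags.

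Total that can be met: 3 + 2 + 2 + 2 + 1 = 10 of 14. This means that each of the ten can be met by some eligible patient. It does not mean that a typical patient meets all ten.

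**Step 3. One illustrative patient (assumed values, constant throughout).** ALT 4.0, AST 3.5, bilirubin 2.5, ALP 1.2. The entry limits are passed (4.0 and 3.5 are below 5; 2.5 is not above 3). Criteria met as written: ALT ≥3, AST ≥3, ALT or AST ≥3, bilirubin >1.5, bilirubin >2, both ALT/AST-plus-bilirubin rows, and potential Hy's Law. That is 8 of 14. Split by baseline status, all 8 fall under already met at baseline and 0 under not met at baseline.

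**Step 4. Whether other summaries show this.** In the shift tables this patient stays in the same band for each analyte: >3 to ≤5 for ALT and AST, >2 to ≤3 for bilirubin, >1 to ≤2 for ALP. Those tables are separate margins. They cannot show that the same patient met the combined criterion before dosing. Change-from-baseline summaries have the same limit.

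**Step 5. Why simply removing patients who met the criterion at baseline would not do.** Take baseline ALT 3.2 and bilirubin 2.1 with ALP ≤2, rising to 12 and 6. The ratios are 12/3.2 = 3.75 and 6/2.1 = 2.86, a marked worsening. The Hy's Law criterion was already met at baseline, so a rule counting only new cases would drop this patient.

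**Step 6. The opposite gap.** Take ALT from 1.3 to 2.9 and bilirubin from 0.6 to 1.4. The ratios are 2.9/1.3 = 2.23 and 1.4/0.6 = 2.33. Both exceed twice baseline, yet no transaminase, bilirubin or combined flag in SAP 6.8.9 is met.

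**The case against.** The strongest reply is that SAP 6.8.9 already deals with baseline. It plans change-from-baseline summaries, shift tables with cuts at 2, 3 and 5×ULN, a listing of flagged patients and a full laboratory listing. Protocol 9.2.2 asks only for actual values and changes from baseline. With up to 40 patients, every potential Hy's Law case can be checked by hand. Adverse-event reporting also takes baseline into account: under Protocol 8.1, findings present at first dose are reported when they worsen, and SAP 6.8.8 summarises these events. Over-inclusive flags are the cautious direction for screening, and exclusion 12 lets the investigator or sponsor keep out a worrying laboratory abnormality.

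Most of this stands for single analytes and for case-by-case review. It does not fill the gap in the combined rows. Adverse-event tables rest on investigator judgement and do not map onto these criteria, exclusion 12 is discretionary, and a listing is not a summary.

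A reader might also infer more than the documents support:

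- That the SAP presents these values as new or treatment-emergent. It does not. The risk is only that the counts are read that way.
- That the SAP breaks a rule in Appendix H. It does not. Appendix H governs the management of individual patients and is not an analysis definition.
- That a number of patients can be given. Assuming that 10% to 20% of 40 enter with ALT or AST ≥3×ULN would give 4 to 8, but that prevalence has no source in the documents. It would also say nothing about Hy's Law, which needs raised bilirubin and limited ALP as well.

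**Conclusion.** The point holds as a reporting weakness. Ten of the 14 liver flags can be met by an eligible patient with no change from entry. For the combined ALT/AST-plus-bilirubin and potential Hy's Law rows, no planned summary shows whether the criterion was already met at baseline. The ALT and AST flags at ≥5× and ≥10×ULN are affected only if values rise between screening and first dose.

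The conclusion rests on the entry limits and flag definitions as written, and on the illustrative patient meeting no other exclusion. How many patients are affected cannot be worked out from the documents. The tables are descriptive, and the primary mortality test is untouched. This is a cheap improvement and not a flaw in the design.

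**What to change.** In SAP 6.8.9:

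1. Keep the any-post-baseline counts, so that no case is lost.
2. Show each flag in two columns, criterion already met at baseline and not met at baseline, using the baseline of SAP 5.3.3. For combined rows, apply the whole combination at baseline.
3. For patients with raised baseline values, also report the number exceeding multiples of their own baseline, so that real worsening is not hidden among those who already met a criterion. The multiples of more than twice baseline in Appendix H could serve, for reporting only. No patient-management rule changes.

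The data are already collected. The cost is a few sentences in the SAP, one re-cut table and some programming. The drawback is small cells once a cohort of up to 40 is divided by baseline status, so the split should be read descriptively alongside the listings.
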